4.7. Sample Size

Assuming an effect size of 0.70, a sample size of 68 subjects (34 subjects per group) will be needed to provide 80% power with a 2-sided test at a 0.05 significance level to detect a difference between losmapimod and placebo in change from baseline in DUX4 activity in affected skeletal muscle after 16 weeks or 36 weeks (depending upon when the muscle biopsy was performed) during the placebo-controlled treatment period. Assuming that approximately 10% of subjects will be non-evaluable, approximately 76 subjects will be randomly assigned at a 1:1 ratio to losmapimod and placebo (38 subjects per group).

4.8. Randomization, Stratification, and Blinding

Subjects will be randomly assigned at the baseline visit (Day 1) to receive losmapimod (active drug) or placebo using a 1:1 allocation ratio. Randomization will be stratified to ensure that the treatment allocation is balanced across FSHD repeat number categories (ie, 1 to 3 repeats versus 4 to 9 repeats). An Interactive Response Technology (IRT) system will be used to administer study drug according to the randomization schedule.

The placebo-controlled treatment period will be performed in a double-blind fashion. The investigator, study staff, subjects, sponsor, and monitor will remain blinded to the treatment until study closure. The sponsor and/or its designee will remain blinded to the subject-level treatment assignment until after all subjects have completed the Week 48 visit (or have discontinued) and the database from the placebo-controlled treatment period has been locked for statistical analyses, after which time they will unblinded. The study drug and its matching placebo are indistinguishable and will be packaged in the same way. There are no tolerability issues that are expected to potentially unblind the assigned study drug.

During the open-label extension, no blinding will be performed (subjects will receive open-label losmapimod); however, subjects will remain blinded to their original treatment assignment from the placebo-controlled treatment period for the duration of the study. The Sponsor and/or its designee may be unblinded after all subjects have completed the Week 48 visit (or have discontinued) and the database from the placebo-controlled treatment period has been locked for statistical analyses.

4.9. Analysis Set

The following analysis sets will be used in the statistical analyses.

4.9.1. Full Analysis Set (FAS)

The FAS will consist of all subjects who are randomly assigned to receive double-blind study drug in the placebo-controlled treatment period. All analyses using the FAS will group subjects according to randomized treatment. The FAS is the main analysis population for the key study endpoints. For the secondary and exploratory endpoints, subjects who already transitioned into the OLE portion under protocol version 3.0 will be analyzed as randomized, in this analysis population.

4.9.2. Per Protocol Set (PPS)

The PPS will consist of all FAS subjects who fulfill all inclusion/exclusion criteria and do not have any significant protocol deviations. All analyses using the PPS will group subjects according to randomized treatment. PPS analyses will be conducted for key study endpoints to assess robustness of key study inferences.

4.9.3. Safety Analysis Set

The Safety Analysis Set will consist of all subjects who receive any study drug. All analyses using the Safety Analysis Set will group subjects according to treatment actually received.

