3.1.1 Placebo-Controlled Treatment Period

During the placebo-controlled treatment period, a total of approximately 76 subjects with FSHD1 will be randomized 1:1 to receive 15 mg PO of losmapimod (n=38) or placebo (n=38) tablets BID for 48 weeks.

At the time of this protocol amendment (10 April 2020), enrollment was completed. A total of 80 subjects have been enrolled. Twelve subjects had rolled over to the OLE portion of the study at Week 24, prior to the COVID-19 pandemic (under protocol version 3.0). At their next clinic visits, these 12 subjects will follow the assessments for the Week 36 visit followed by the Week 48 visit in the placebo-controlled portion of the study under the COVID-19 Pandemic Emergency protocol version 4.0. These subjects will continue to receive open label losmapimod during this time.

Subjects will participate in the placebo-controlled treatment period for approximately 53 weeks, including the following:

Fulcrum Therapeutics	Losmapimod
Protocol FIS-002-2019, Version 4.0 (COVID-19 Pandemic Emergency Amendment)	10 April 2020

- a 4-week screening period: Day -28 until Day -1 before the first study drug administration
- a 48-week placebo-controlled treatment period
- for subjects who choose not to roll over into the OLE, a safety follow-up visit 7 days (± 3 days) after the last dose of study drug (OLE visits and procedures are described in [Section 3.1.2](#))

The 12 subjects who rolled over to the OLE portion of the study at Week 24, prior to the COVID-19 pandemic (under protocol version 3.0), participated in the placebo-controlled portion of the study for approximately 29 weeks including the following:

- a 4-week screening period: Day -28 until Day -1 before the first study drug administration
- a 24-week placebo-controlled treatment period
- for subjects who chose not to roll over into the OLE, a safety follow-up visit 7 days (± 3 days) after the last dose of study drug (OLE visits and procedures are described in [Section 3.1.2](#))

During the placebo-controlled treatment period, subjects will be asked to attend the study clinic at each scheduled visit ([Table 13-1](#)). Study drug (losmapimod or placebo) will be administered BID and should be taken with food.

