Facioscapulohumeral muscular dystrophy (FSHD) is a rare disabling disease with an estimated worldwide population prevalence of between 1:15,000 and 1:20,000 ([Statland and Tawil, 2014](#)), or approximately 16,000 to 21,000 affected individuals in the United States. FSHD is characterized by descending progressive skeletal muscle weakness affecting the face, shoulders, arms, and trunk, followed by weakness of the distal lower extremities and pelvic girdle. FSHD is caused by aberrant overexpression of the double homeobox 4 (DUX4) gene, a homeobox transcription factor. DUX4 is located within D4Z4 macrosatellite repeats on chromosome 4q35 and is not normally expressed in adult skeletal muscle when the number of repeats is >10. Approximately 95% of patients with FSHD have type 1 (FSHD1), in which the D4Z4 repeat array is contracted to 1 to 10 units on one allele ([Lemmers et al, 2010](#); [Statland and Tawil, 2014](#)). FSHD patients carrying a smaller number of repeats (1 to 3 units) are, on average, more severely affected ([Tawil et al, 1996](#)).

There are currently no approved disease-modifying treatments for FSHD. Fulcrum is developing losmapimod, a selective p38 α/β inhibitor, which is predicted to reduce DUX4 in affected skeletal muscle. It is anticipated that the proposed human dose of losmapimod for FSHD at 15 mg orally (PO) twice daily (BID) will provide drug concentrations in skeletal muscles sufficient to significantly inhibit p38 α/β and reduce aberrant expression of DUX4.

The term study drug that is being used throughout this document refers to losmapimod and/or placebo.

2. Objectives

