4.1. Reporting Conventions

All data summaries, unless otherwise noted, will be presented by treatment group:

- Losmapimod 15 mg BID
- Placebo BID

The following conventions will be used for all the data presentations and analyses unless otherwise specified.

Appropriate descriptive statistics will be computed and displayed for both continuous and categorical variables. For continuous and quantitative variables, summaries will include n (number of subjects with non-missing data), mean, standard deviation (SD), Q1 (first quartile), Q3 (third quartile), median, minimum and maximum. Reporting conventions for descriptive statistics will follow the [REDACTED] Standard TLF Guidelines. For categorical variables, summaries will include the number and percentage of subjects who are in a particular category. Percentages will be computed based on the number of non-missing data points for patients in the applicable analysis set. Reporting of percentages will follow the [REDACTED] standard TLF Guidelines.

A total column will be presented for all demographic, baseline characteristic, baseline disease characteristic, protocol deviation, and prior and concomitant medication summaries.

All data will be listed by treatment group, FSHD repeat number category, subject ID, Ricci score, sex and visit date, if available. Any repeat assessments or additional assessments, along with any unscheduled visits, will be presented in the listings. Sort order of data listings will be treatment group, FSHD repeat number category, subject ID, and visit date, if available.

Statistical tests will be 2-sided and will be conducted at the significance level provided in [Table 12-1](#)), unless otherwise specified. P-values will be reported to 4 decimal places, with p-values less than 0.0001 reported as “<0.0001”.

All analyses will be performed using Statistical Analysis Software (SAS®, release 9.4 or higher). A separate document as an appendix to this SAP will contain the tables, listings, and figure (shells).

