4.4. Visit Windows

In general, data for assessments that are collected by scheduled visits will be mapped to visits that appear in the schedule of assessments per the protocol using the actual study day of assessment. Data mapped to scheduled visits will include all data collected up to the reporting cut-off date and may include withdrawal visits and unscheduled visits.

Visit windows will be continuous from the midpoint between two consecutive study visits and will be dependent on the schedule of assessments for each variable independently. The exception is the Week 16 analysis window, which has been extended to allow for potentially delayed visit due to COVID-19 pandemic. An example of the Vital Signs visit window is given in [Table 4-1](#). Visit windows for each variable will be constructed in the same manner.

Table 4-1: Visit Windows

Study Visit	Scheduled Day	Analysis Window
Baseline	1	≤ 1
Week 4	28	>1 to ≤ 56
Week 12	84	>56 to ≤ 98
Week 16	112	>98 to ≤ 154
Week 24	168	>154 to ≤ 210
Week 36	252	>210 to ≤ 294
Week 48	336	>294 to ≤ 378

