7.2. Study Treatments

7.2.1. Extent of Exposure

Duration of exposure is defined as the total number of days a subject is exposed to study drug and will be presented as the total number of days from the first dose date (Day 1) to the last dose date (ie, calculated as the date of last dose minus the date of first dose + 1). If the last dose date is missing, or if a subject is lost to follow-up, but the drug accountability log confirms that the subject has taken study drug, the visit date following the last completed drug accountability log will be used.

The exposure to study drug will also be characterized by cumulative dose, which is defined as the cumulative number of tablets taken.

The duration of exposure to study drug by treatment group will be summarized for all subjects in the Safety Analysis Set and will be presented in a table using summary statistics. The duration of exposure will then be classified into one of the following categories: < 8 weeks, \geq 8 weeks, \geq

16 weeks, \geq 24 weeks, \geq 36 weeks and \geq 48 weeks and will be presented as the number and percentage of subjects in each duration category. Percentages will be computed from the number of subjects in the Safety Analysis Set.

The total cumulative dose in mg will be defined as the total number of tablets taken across all study days times 7.5 mg. Average daily dose will be defined as cumulative dose divided by total days on study drug. The average daily dose and cumulative dose will be summarized using summary statistics.

A summary of each subject's exposure will also be presented in a listing.

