8.5. Inflammatory, Immune, Apoptotic, and Muscle Disease Transcripts

The analysis of these exploratory endpoints will be described in a separate document.

9. Safety Analysis

All summaries of safety data will use the Safety Analysis Set and will be presented by treatment.

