9.1. Adverse Events

A treatment-emergent AE (TEAE) is defined as an AE that meets any of the following conditions:

- begins on or after the first dose of study drug and before the stop of study drug + 7 days;
- begins before the first dose of study drug and worsens in severity on or after the first dose of study drug and before the stop of study drug + 7 days;
- is completely missing an onset date and end date;

- is completely missing an onset date and the end date is on or after the first dose of study drug.

For the purpose of inclusion in TEAE tables, incomplete AE onset and end dates will be imputed as follows:

Missing onset dates (where UK and UKN indicate unknown or missing day and month respectively):

- UK-MMM-YYYY: If the AE month and year are different from the month and year of the first dose of study drug, assume 01-MMM-YYYY. If the month and year are the same as the first dose of study drug month and year and the AE end date (after any imputation) is on or after the first dose of study drug, then assume the date of the first dose of study drug. If the AE month and year are the same as the first dose of study drug month and year and the AE end date (after any imputation) is prior to the first dose of study drug, then assume the end date for the onset date.
- DD-UKN-YYYY/UK-UKN-YYYY: If the AE year is different from the year of first dose of study drug, assume DD-JAN-YYYY/01-JAN-YYYY of the collected year. If the AE year is the same as the first dose of study drug year and the AE end date (after any imputation) is on or after the first dose of study drug, then assume the date of the first dose of study drug. If the year is the same as the first dose of study drug and the AE end date (after any imputation) is prior to the first dose of study drug, then assume the end date for the onset date.

Missing end dates (where UK and UKN indicate unknown or missing day and month respectively):

- UK-MMM-YYYY: Assume the last day of the month;
- DD-UKN-YYYY: Assume DD-DEC-YYYY;
- UK-UKN-YYYY: Assume 31-DEC-YYYY.

All AEs will be classified by SOC and PT according to the MedDRA version 22.0 or higher.

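### The SAP does not carry the protocol's split of safety data by period into a cut at the first open-label dose, so read literally a placebo subject who rolled over at Week 24 has both treatments reported in one column

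*SAP*

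**What the plan says.** Protocol 3.1.1 reports 80 subjects enrolled, of whom 12 rolled over to the open-label extension (OLE) at Week 24 under version 3.0. They follow the Week 36 and Week 48 assessments of the placebo-controlled portion, and "These subjects will continue to receive open label losmapimod during this time".

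The SAP rules that decide where their safety data go are these:

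- **Scope (opening of section 9):** "All summaries of safety data will use the Safety Analysis Set and will be presented by treatment".
- **Columns (4.1):** "All data summaries, unless otherwise noted, will be presented by treatment group". Two groups follow, losmapimod and placebo.
- **Grouping (4.9.3):** "All analyses using the Safety Analysis Set will group subjects according to treatment actually received".
- **Treatment-emergent window (9.1):** an event counts if it "begins on or after the first dose of study drug and before the stop of study drug + 7 days". A second limb, for worsening of an earlier event, has the same end.
- **Meaning of study drug (1):** "The term study drug that is being used throughout this document refers to losmapimod and/or placebo".
- **Exposure (7.2.1):** "Duration of exposure is defined as the total number of days a subject is exposed to study drug", calculated from first to last dose, with categories up to 48 weeks or more.
- **Visit windows (4.4):** "Data mapped to scheduled visits will include all data collected up to the reporting cut-off date". The Week 48 window closes at day 378.
- **Laboratory shifts (9.2.1, 9.2.2):** baseline against the maximum post-baseline value.

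Protocol 7.6.6 analyses placebo-period safety on the safety analysis set and OLE safety on the open-label analysis set. The SAP addendum changes none of the rules listed above in a way that adds a cut.

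**The concern.** A subject randomised to placebo who rolled over has actually received both treatments. The grouping rule does not say which column applies, and no rule divides the subject's time. Because study drug includes either treatment, the switch closes neither the treatment-emergent window nor the exposure clock.

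Whichever column is chosen is wrong for about half of that subject's 48 weeks. Under placebo, events on losmapimod count as placebo events. Under losmapimod, placebo time and placebo events count as losmapimod. Either way the contrast between arms is blurred.

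This matters because Protocol 3.2.2 gives long-term safety against placebo as a reason for extending the randomised period to 48 weeks, and the version 4.0 amendment elevated safety among the secondary objectives.

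**Working it through.** The plan gives no figure for open-label exposure in the safety tables, so there is none to reproduce.

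**Where the period ends.** Two statements disagree.

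- Protocol 4.2 ends the placebo-controlled period, for a subject rolling over, at completion of the Week 48 visit, and starts the OLE after it. On that definition Weeks 24 to 48 of the 12 subjects fall inside the placebo-controlled period.
- Protocol 3.1.1 and SAP 3.1 give these 12 a 24-week placebo-controlled period. On that definition the same weeks are OLE time.

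Limiting the SAP to the placebo-controlled period therefore does not settle the cut.

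**Inputs from the documents.** 80 enrolled, 1:1 allocation, 12 roll-overs at Week 24, follow-up to Week 48.

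**Assumptions.** 40 per arm, everyone followed for 48 weeks, no dropout. The arm split of the 12 is not given. If 12 are drawn at random from 80 with 40 on placebo, the expected number on placebo is 6, and the 95% hypergeometric range is 3 to 9.

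**Time per subject.** 48 − 24 = 24 weeks of open-label losmapimod, and 24/48 = half of the subject's time. For by-visit data running to day 378, with Week 24 at day 168, it is at most (378 − 168)/7 = 30 weeks.

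**Share of person-time, for k placebo roll-over subjects.**

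- Placed under placebo: losmapimod time is 24k, and the column total is 40 × 48 = 1,920 person-weeks. That total includes the losmapimod weeks.
- Placed under losmapimod: placebo time is 24k, and the column total is (40 + k) × 48.

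| k | Misplaced person-weeks | Share of placebo column | Share of losmapimod column |
|---|---|---|---|
| 3 | 72 | 72/1,920 = 3.8% | 72/2,064 = 3.5% |
| 6 | 144 | 144/1,920 = 7.5% | 144/2,208 = 6.5% |
| 9 | 216 | 216/1,920 = 11% | 216/2,352 = 9.2% |

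**Share of subjects.** The adverse event tables in SAP 9.1 report numbers and percentages of subjects, so this scale is closer to what will be printed. If these subjects stay under placebo, 6/40 = 15% of that column (3/40 = 7.5% to 9/40 = 22.5%) could have a misattributed event. One such subject moves a placebo percentage by 1/40 = 2.5 points.

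**What is exposed.** Whole-period adverse event tables, exposure, maximum post-baseline laboratory shifts, the liver abnormality counts, and the Week 36 and Week 48 summaries. By-visit summaries through Week 24 are essentially unaffected.

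**The case against.** The strongest reply is that separation is clearly intended. Besides 7.6.6, Protocol 7 has analyses generated separately for the two periods. Protocol 7.4 admits subjects to the open-label analysis set after 24 weeks, not 48, of placebo-controlled treatment plus one open-label dose, so the 12 qualify from roll-over. SAP 1 leaves the OLE to a separate SAP. The table shells and the OLE SAP are not available here and could contain a cut.

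This stands as evidence of intent. A reader might infer that the sponsor has decided to count open-label losmapimod as placebo experience, and the documents do not support that. What they show is an intended split that never becomes a date rule, beside SAP definitions that give a mixed result when followed exactly.

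A second reply is that SAP 15.8 already repeats most safety tables for the Open-label Losmapimod (Pre-COVID-19) set. That helps a reader to see the 12 subjects. However, SAP 4.9.6 defines that set by subject, not by time, so its tables take nothing out of the main ones and would themselves include the first 24 blinded weeks. The analysis excluding cross-over subjects in SAP 8.2.1 covers only the primary endpoint, and the as-randomised rule for these subjects in SAP 4.9.1 applies only to the full analysis set.

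A third reply is that person-time shares are not the bias in any planned statistic. That is correct. The shares measure how much exposure is misplaced, and no effect on incidence has been shown.

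**Conclusion.** The point holds as a gap between the protocol's period split and the SAP's definitions. As written, about 24 weeks of placebo and 24 weeks of losmapimod are reported together for each placebo subject who rolled over at Week 24. The central estimate is 144 misplaced person-weeks, and its share depends on a column choice that the SAP leaves open. It rests on an assumed arm split, 40 per arm and full follow-up.

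A reader might also infer that a safety signal will be hidden, or that the primary result is compromised. Neither follows. The column is unspecified, no incidence effect can be calculated from the documents, and the 12 have no Week 36 biopsy, so the primary endpoint uses no biopsy taken after their switch. The change should be made, but it does not threaten the primary analysis.

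**What to change.** In SAP 7.2.1 and section 9:

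1. Group subjects by the double-blind treatment received, and end the by-arm treatment-emergent, laboratory, vital sign, ECG and exposure windows at the first open-label dose.
2. Assign events that start or worsen on or after that dose to the open-label period, with no 7-day tail past it.
3. Restrict the Open-label Losmapimod (Pre-COVID-19) safety tables to data from that dose onward, and state the baseline they use.
4. Show person-time for each period, because follow-up will differ between subjects.

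Protocol 4.2 and 3.1.1 should be reconciled on when the placebo-controlled period ends for the 12. The same cut would also close the windows for subjects who roll over at Week 48, for whom the SAP's definitions likewise give no end at the switch.

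The cost is one rule, one data flag and a start date for open-label tables that are already listed. There is a small loss. Post-Week-24 time of roll-over subjects randomised to losmapimod, 6 × 24 = 144 person-weeks on the same assumption, also moves to the open-label tables. Each column then keeps 1,920 − 144 = 1,776 person-weeks.

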4.9.4. Pharmacokinetics Analysis Set

The PK Analysis Set will consist of all subjects who receive at least 1 dose of losmapimod and have evaluable PK data for losmapimod.

4.9.5. Pharmacodynamics Analysis Set

The PD Analysis Set will consist of all subjects who receive at least 1 dose of losmapimod and have evaluable PD data for losmapimod.

4.9.6. Open-label Losmapimod (Pre-COVID-19) Analysis Set

This analysis set will consist of subjects who were already transitioned into open-label losmapimod under version 3.0 of the protocol. This analysis set will be used for sensitivity analysis, to assess secondary/exploratory endpoints in this subset of subjects.

5. Subject Disposition

